2. LAY SUMMARY

Backwards walking has been shown to improve balance and walking in patients who have knee Osteoarthritis. We don't know if these benefits may also be seen after surgery with patients who have had a hip or knee replacement because of Osteoarthritis. This study will look to see if it is possible to conduct a bigger study into how effective backwards walking may be after joint replacement. Patients who come to the Nuffield Orthopaedic Centre in Oxford for a hip or knee replacement will be invited. They will be placed into one of two groups at random: a group where they have a course of physiotherapy plus a backwards walking programme or a group where they have a course of physiotherapy. The physiotherapy will last for 12 weeks and those who take part will take part in two study assessments. The first will be before any treatment and patients will complete five measures and also be issued with a simple tick box diary to complete over the 12 weeks. The second assessment will be after the treatment and will involve the same 5 measures and the diaries will be collected in. Participants at this assessment will also be asked if they would like to take part in an interview for the study. This is to see what the patients thought of the study. During the study the researcher will record things like how many patients say 'yes' to the study and how many participants drop out of the treatment to understand if a bigger study could take place.

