6. OBJECTIVES AND OUTCOME MEASURES

Objectives	Outcome Measures	Timepoint(s) of evaluation of this outcome measure (if applicable)

Primary Objective To test the procedures and processes of the trial and to estimate parameters for the main trial sample size calculation
	
 • Berg Balance Scale (BBS) (to calculate sample size) – Static and dynamic balance activities of varying difficulty are performed to provide a measure of falls risk and balance • Participant recruitment figures • Participant retention figures • Randomisation acceptability • Number of protocol violations from fidelity checks • BW programme diary to provide a measure of adherence • Participant safety through recording any falls and injuries whilst completing the BW programme • Qualitative interviews to determine acceptability of intervention and delivery with participants and physiotherapists 	Baseline and 3 months

Secondary Objectives To examine the consistency of the effects of the backwards walking programme on falls risk, balance, strength and gait speed following hip and knee joint arthroplasty
	
 • Four Square Step Test (FSST)- a test of dynamic balance that clinically assesses a person's ability to step over objects forward, sideways, and backwards • 2 minute walk test (2MWT)- assesses walking distance • 30 second chair rise test - assesses sit to stand ability and provides a measure of lower limb strength and dynamic balance. • Activities-specific Balance confidence scale (ABC) - self-reported measure of confidence in performing various ambulatory activities without falling • Falls diary - records the frequency of falls 	Baseline and 3 months

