7. STUDY DESIGN

This study is a mixed methods design. The quantitative study will be a randomised single blinded design. Up to 40 participants will be recruited from a single site at the Nuffield Orthopaedic Centre in Oxford. After recruitment baseline outcome measures will be taken. Block randomisation will then be used to balance stratification factors (hip or knee arthroplasty) into either the intervention or control group. The participant will receive their physiotherapy intervention or control at the Nuffield Orthopaedic Centre which will last up to 12 weeks. Once the first 5 participants randomised into the intervention arm have been recruited the study will be halted whilst all adverse event data is collected to ensure participants have not fallen when completing the intervention. If the study team is happy the intervention is not causing any adverse events, then the next five participants will be recruited and again the study will halt whilst their adverse event data is collected. This will continue until all 20 participants for the intervention group are recruited. Outcome measures will be repeated at 12 weeks once the treatment has ceased. This will be the final data collection point for the study.

The qualitative element of the study will involve semi structured interviews. This will take place after the participants have completed their 12 week follow up and physiotherapists have completed the intervention delivery. We will interview to a point of theoretical saturation¹⁶, and anticipate that up to 10 participants and 5 physiotherapists will allow us to develop useful themes.

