9.3. Informed Consent

Informed consent will be taken by an experienced physiotherapy researcher who has completed specific training in taking consent including Good Clinical Practice Training and has experience taking consent for participating in physiotherapy research.

The participant must personally sign and date the latest approved version of the Informed Consent form before any study specific procedures are performed.

Written and verbal versions of the Participant Information and Informed Consent will be presented to the participants detailing no less than: the exact nature of the study; what it will involve for the participant; the implications and constraints of the protocol; the known side effects and any risks involved in taking part. It will be clearly stated that the participant is free to withdraw from the study at any time for any reason without prejudice to future care, without affecting their legal rights, and with no obligation to give the reason for withdrawal.

The participant will be allowed as much time as wished to consider the information, and the opportunity to question the Investigator, their GP or other independent parties to decide whether they will participate in the study. Written Informed Consent will then be obtained by means of participant dated signature and dated signature of the person who presented and obtained the Informed Consent. A copy of the signed Informed Consent will be given to the participant. The original signed form will be retained at the study site.

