9.8. Subsequent Visits

As this is a feasibility pilot study the main aims are not to assess the effectiveness of the intervention but to trial the acceptability and feasibility of the study protocol and pilot its delivery at the Nuffield Orthopaedic Centre in Oxford. For this reason the main assessments for the study relate to recruitment, retention and acceptability. The research clinician will therefore collect data throughout the trial on the number of patients screened, the number that consented, the reason for not consenting, the number of drop outs, the availability of the outcome measure data and the standard deviation of the BBS in order to estimate the sample size. The acceptability of the intervention will be measured through collection of the BW programme diary which will provide a measure of adherence. Participants will also be invited to take part in an interview to determine the study acceptability.

Fidelity checks

Fidelity checks will be made by a member of the study team who is not blinded to treatment allocation to ensure adherence to the study protocol from the recruiting and treating clinicians. These will take place mid-way through study recruitment once approximately 20 participants have been randomised.

12 week follow up

Participants will be followed up at 12 weeks for the final assessment. Participants will be asked to return to the physiotherapy clinic or where possible this appointment will tie in with their final physiotherapy appointment at 12 weeks. The outcome measure assessments will be the same as at baseline and the research clinician will ensure they collect in the falls diary and if applicable BW programme diary.

Qualitative interviews

Patients taking part in the study, and treating clinicians, will be invited to take part at the in a semi-structured interview to determine if the study procedures and trial design were acceptable to participants. This will take place after the participants have completed their 12 week follow up and physiotherapists have completed the intervention delivery.

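### Participant interviews and collection of the BW diary both depend on the 12-week visit, so those who leave the study or miss that visit have no stated route to either

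*Combined protocol and SAP*

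**What the plan says.** **Interviews.** Sections 7 and 9.8 give the same timing: "This will take place after the participants have completed their 12 week follow up and physiotherapists have completed the intervention delivery". The lay summary (section 2) places the invitation at the second assessment: "Participants at this assessment will also be asked if they would like to take part in an interview for the study". On numbers, section 7 plans to interview until saturation, and the authors "anticipate that up to 10 participants and 5 physiotherapists will allow us to develop useful themes".

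**BW diary.** It is issued at the first physiotherapy appointment (9.7) and filled in at home (9.6.1). At the 12-week follow-up "the research clinician will ensure they collect in the falls diary and if applicable BW programme diary" (9.8). The lay summary agrees: "The second assessment will be after the treatment and will involve the same 5 measures and the diaries will be collected in". Section 9.6.1 allows up to four review appointments but does not say that the diary is collected or copied at them.

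**Role of the two measures.** Section 6 lists both under the primary objective: "BW programme diary to provide a measure of adherence" and "Qualitative interviews to determine acceptability of intervention and delivery with participants and physiotherapists". Section 11.2 names the diary as the adherence measure, asks whether any participants fail to complete the intervention, and says that the qualitative study will look further into these issues.

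**Leaving.** Under section 9.10, people who stop the study treatment are encouraged to stay in follow-up. For those who withdraw consent or whose trial participation is ended, data gathered up to that point are kept unless they ask for destruction, and nothing further is contributed. A withdrawal form and a reason are completed, and randomised participants who withdraw are not replaced. Section 9.3 promises that participants may leave "with no obligation to give the reason for withdrawal".

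**The concern.** Section 9.8 says that the study's main assessments are recruitment, retention and acceptability. Two of the acceptability measures, the diary and the participant's own account, are gathered at or after one visit. A person who has left by then, or does not attend, supplies neither under the procedures as written. Leaving may plausibly be related to how acceptable or manageable the programme was, so the people missing could be among the most informative on that question.

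A main-trial team would then read adherence and acceptability findings that describe mainly attenders. Section 11.2 states no denominator for adherence, so a figure from returned diaries alone could be reported without showing how many were missing.

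**Working it through.** The plan states no figure for adherence, diary return or drop-out, so there is none to reproduce. The check is a comparison of the text, followed by a bound.

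**Step 1: who keeps a route, on the stated procedures**

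| Participant | Diary collected? | Interview? | Other information |
|---|---|---|---|
| Completes programme, attends week 12 | Yes (9.8) | Yes (7, 9.8) | Full |
| Stops programme only, attends week 12 | Yes | Yes | Full |
| Still in the study, misses week 12 | No route stated | No route stated | Treatment logs, review appointments, physiotherapist interviews |
| Leaves the study before week 12 | No route stated | No route stated | As above, plus drop-out count, withdrawal form and reason |

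The last column is partial information. None of it is a session record kept by the participant or the participant's own full account.

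**Step 2: what section 9.10 leaves open**

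- *A diary filled in before leaving but not yet handed in.* It could count as data already collected, which are kept, or as further data, which are not contributed. The text does not say.
- *Which withdrawal routes continue follow-up.* Discontinuation by the chief investigator is described as being from the study interventions, and people off treatment are encouraged to stay in follow-up. One of the listed grounds, however, is being unable to keep complying with trial procedures, and those whose trial participation is ended give no further data. The treating clinician may withdraw someone from the study itself. The text does not settle which of these people are still followed.

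**Step 3: bound on mean adherence**

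Inputs: n = 20 randomised to BW (11.3). Assumed: k diaries not returned, and mean adherence A among those returned, with each person's adherence expressed on a 0–100% scale.

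- Lower bound (all missing at 0%): (20 − k) × A / 20
- Upper bound (all missing at 100%): lower bound + 100k / 20
- Width: 100k / 20 = 5k percentage points, whatever A is

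| k missing | A = 80% | A = 60% | Width (points) |
|---|---|---|---|
| 2 | 18 × 80/20 = 72 to 82% | 18 × 60/20 = 54 to 64% | 10 |
| 4 | 16 × 80/20 = 64 to 84% | 16 × 60/20 = 48 to 68% | 20 |
| 6 | 14 × 80/20 = 56 to 86% | 14 × 60/20 = 42 to 72% | 30 |

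Possible error of a figure from returned diaries only, at k = 4:

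- A = 80%: 80 − 64 = 16 points too high, or 84 − 80 = 4 points too low, at the extremes.
- A = 60%: 60 − 48 = 12 points too high, or 68 − 60 = 8 points too low.

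The values of k and A are illustrations. Only n = 20 comes from the documents.

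**The case against.** **The affected group is narrow.** This stands. People who stop only the programme can still attend, return a diary and be interviewed. For those who withdraw consent, ending data contribution is a protection rather than an oversight. For those who merely miss the visit, the text is silent and forbids nothing. The consent form, leaflet and withdrawal form are not in the text reviewed and might cover diary return.

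**The question in section 11.2 can be answered in part as written.** This also stands. Someone who stopped the programme but attends at week 12 did fail to complete it and can be interviewed. Drop-outs and, where possible, their reasons are recorded independently of that visit, and physiotherapists are interviewed. A reader might infer that non-completion cannot be studied at all; the documents do not support that. What is missing is the leavers' own accounts and diary entries.

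**The timing has a plausible purpose.** Interviewing after the final assessment keeps discussion of the programme away from outcome measurement and from the blinded assessor (9.5). That is a good reason to keep the timing for everyone still in follow-up. It does not apply to someone who will have no final assessment. The sentence might describe sequence rather than eligibility, but the invitation at the visit in the lay summary weakens that reading.

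**The bound is generic.** Five points per diary is simply 1/20 and would hold in any arm of 20. No adherence threshold or progression rule is stated, so no planned decision can be shown to change. This is accepted and limits the severity.

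**Conclusion.** The point holds as a minor one. Under the stated procedures, two measures listed under the primary objective would be described mainly from week-12 attenders, and other records fill the gap only in part. The uncertainty in mean adherence for the whole BW arm is 5 percentage points per unreturned diary. This rests on 20 being randomised to BW and on adherence being scored from 0 to 100% per person.

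Three stronger readings are tempting and not supported:

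- *That reported adherence will be too high.* The documents give neither a drop-out rate nor an adherence rate, and the bound allows error in both directions.
- *That follow-up simply continues after the chief investigator discontinues someone.* Section 9.10 only encourages continuation for people off treatment, and bars further data from those whose participation is ended.
- *That 10 participant interviews is a cap, so leavers could be included with none added.* Section 7 interviews to saturation and treats that number as an expectation.

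The pilot remains valid for its purposes. The change is worth making because it is cheap and bears on what the main trial would learn.

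**What to change.** 1. **Section 9.8, diary.** When a participant leaves the study or misses week 12, ask for the BW diary with the participant's agreement, for example by post.
2. **Sections 7 and 9.8, interview.** Offer an opt-in interview to those who will not reach week 12. Cover it in the consent form and leaflet, have it done by someone other than the blinded assessor, and word it to fit the limit on further data in 9.10 and the freedom in 9.3 not to give a reason. Keep the present timing for everyone else. Section 9.8 already has an unblinded team member for fidelity checks, so a suitable person may be available.
3. **Section 11.2, reporting.** Give the number of diaries returned out of all randomised to BW beside the adherence figure, and add a sensitivity result that counts unreturned diary days as not done. That is the lower bound shown above.
4. **Section 9.10, wording.** Reconcile the text on whether entries made before leaving are data already collected or further data, and on which withdrawal routes continue follow-up. Who is stopped or withdrawn remains a matter for the chief investigator and the treating clinician.

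**Cost.** A protocol amendment with approval where needed (16.3), wording in the consent form and leaflet, postage, and possibly a few more interviews. Some leavers will decline, so the gap will narrow rather than close, and reported adherence may look less favourable. Item 3 needs no extra data.

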9.9. Sample Handling

No samples will be taken.

9.10. Early Discontinuation/Withdrawal of Participants

Each participant has the right to withdraw from the study at any time. In addition, the Chief Investigator (CI) may discontinue a participant from the study interventions at any time if the investigator considers it necessary for any reason including:

- Ineligibility (either arising during the study or retrospectively having been overlooked at screening)
- A significant protocol deviation
- A significant non-compliance with treatment regimen or study requirements
- An adverse event which requires discontinuation of the study intervention or results in inability to continue to comply with trial procedures

It will be the sole responsibility of the CI to determine whether investigator-led discontinuation occurs or not.

The treating clinician may withdraw a participant from the study if they feel it would not be clinically appropriate for them to continue.

If the participant has withdrawn from study treatment then they will be encouraged to continue with the follow-up.

Participants who wish to withdraw consent for the study or whose participation from the trial is discontinued will have de-identifiable data collected up to the point of that withdrawal of consent, included in the analyses, unless the participant specifically asks for all data collected to be destroyed. The participant will not contribute further data to the trial and the withdrawal CRF will be completed which documents the level of withdrawal. The reason for withdrawal will also be recorded. Participants who withdraw once they have been randomised will not be replaced.

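### Section 9.10 is inconsistent on what a staff-led stop ends; taken literally, a treating clinician's decision can cost a still-consenting participant the 12-week assessment

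*Combined protocol and SAP*

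**What the plan says.** Section 9.10 describes several ways out of the study and does not use the same object for each.

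- **CI-led stop.** The CI "may discontinue a participant from the study interventions at any time if the investigator considers it necessary". The object is the intervention.
- **Clinician-led stop.** "The treating clinician may withdraw a participant from the study if they feel it would not be clinically appropriate for them to continue". The object is the study.
- **Follow-up after a stop.** "If the participant has withdrawn from study treatment then they will be encouraged to continue with the follow-up". This is tied to stopping treatment.
- **End of data collection.** The closing paragraph covers "Participants who wish to withdraw consent for the study or whose participation from the trial is discontinued". These people "will have de-identifiable data collected up to the point of that withdrawal of consent, included in the analyses", unless they ask for their data to be destroyed. It continues: "The participant will not contribute further data to the trial and the withdrawal CRF will be completed which documents the level of withdrawal". Staff also note why the person left, and randomised participants who withdraw are not replaced.

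Section 9.8 places the final assessment at 12 weeks, when the falls diary and, where applicable, the backwards walking diary are collected. Sections 7 and 9.8 give no other post-baseline assessment. Section 9.8 also lists the data to be gathered for feasibility, among them "the number of drop outs, the availability of the outcome measure data and the standard deviation of the BBS". Section 6 places both retention and the BBS under the primary objective.

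**The concern.** Stopping an exercise programme and leaving a study are different events, and a feasibility trial needs to tell them apart. Section 11.2 does so: whether participants fail to complete the intervention comes under acceptability, and drop-outs come under retention. Section 9.10 blurs the two when the decision is the treating clinician's. If a physiotherapist judges that someone should not go on, and staff apply the wording as it stands, a participant who was willing to return at week 12 may not be invited.

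Two things are then at stake. The first is a week-12 record that cannot be recovered later, with the diaries that would have been handed in at that visit. The second is the meaning of the retention figure carried forward to the main trial, which could mix participants' unwillingness to return with staff decisions to stop the exercise.

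**Working it through.** The plan gives no figure for this point, so the check is mainly textual, followed by a short calculation of size.

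**Step 1. Follow the text for each route out (all Section 9.10).**

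| Route | What is stopped | Is follow-up kept? |
|---|---|---|
| CI decision | Study interventions | Yes, encouraged, if treated as leaving treatment |
| Treating clinician decision | The study | Not stated; taken literally, falls under the closing paragraph |
| Participant stops treatment | Study treatment | Yes, encouraged |
| Participant withdraws consent | Consent | No further data, as it should be |

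The second row is the problem. The closing paragraph joins consent withdrawal and discontinued participation with the word *or*. A participant withdrawn from the study by a clinician fits the second half of that pair while still consenting.

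**Step 2. Look for anything that settles it.** The CRF records a level of withdrawal, but the levels are not defined. Section 9.8 says participants are followed up at 12 weeks and makes no mention of withdrawal. Nothing states explicitly that a participant withdrawn by a clinician keeps the visit. Section 9.10 also makes the CI solely responsible for investigator-led discontinuation, which sits awkwardly beside the clinician's separate power.

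**Step 3. Size for retention.** Section 11.3 gives 20 per group, and 2 × 20 = 40. One exit counted as a loss changes retention by 1/40 = 2.5 percentage points. Three would change it by 3/40 = 7.5 points.

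**Step 4. Size for the SD of the BBS at week 12.** For a pooled two-arm SD with df = n − 2, the 95% limits as multiples of the observed SD are

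lower = √(df / χ²(0.975, df)), upper = √(df / χ²(0.025, df)).

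| Assessed at week 12 | df | χ²(0.975) | χ²(0.025) | 95% limits (× SD) |
|---|---|---|---|---|
| 40 | 38 | 56.896 | 22.878 | 0.817 to 1.289 |
| 39 | 37 | 55.668 | 22.106 | 0.815 to 1.294 |
| 37 | 35 | 53.203 | 20.569 | 0.811 to 1.304 |

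For example, with 40 assessed, √(38/56.896) = 0.817 and √(38/22.878) = 1.289. Losing three assessments moves the upper limit by 1.304 − 1.289 = 0.015 of the SD.

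The exits of one and three are illustrative, because the documents give no withdrawal rate. The limits assume normal data and loss unrelated to the score.

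**The case against.** The strongest reply is that Section 9.10 already intends the sensible rule. The sentence encouraging continued follow-up comes straight after the clinician's power and can be read as covering it. Treating clinicians deliver physiotherapy, while a separate blinded research clinician does the assessments (Section 9.5), so a judgement that continuing is inappropriate is most plausibly a judgement about treatment. The closing paragraph dates the cut-off from withdrawal of consent, and a graded level of withdrawal would have little purpose if every exit ended all data collection. All of this stands. It makes the milder reading credible, but it does not remove the literal one.

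A reader might infer three stronger things, none of which the documents support:

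- **That the protocol plainly removes follow-up from consenting participants.** It does not; the text is inconsistent and leaves both readings open.
- **That each such exit would be counted as a drop-out.** Drop-out is not defined and no counting rule is given. Reason and level of withdrawal are recorded, so these exits can be reported apart from participants' own choices. No retention threshold is set on which 2.5 points would turn.
- **That the BBS SD, or the comparison between arms, is compromised.** Baseline BBS is taken before allocation and is untouched, and the plan does not confine the SD to week 12. The treating clinician is unblinded, so exits could in principle differ by arm. However, Section 11.2 says that measuring efficacy is not the aim, and nothing indicates how often such exits would occur.

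**Conclusion.** The point holds as an inconsistency with a small and avoidable cost. Section 9.10 gives the treating clinician a wider power than the CI and links discontinued participation to the end of data collection. Two members of staff could therefore handle the same consenting participant differently, one keeping the week-12 visit and the other cancelling it.

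Per exit, the possible cost is one week-12 record with its diary collection and 2.5 points of apparent retention. The cost to SD precision is negligible. This rests on staff applying the literal reading, and on the participant being willing to attend and safe to assess; some would be unable to do the BBS in any case. The number of exits is unknown, and with none nothing is lost. Recorded reasons can identify these exits afterwards, but they cannot replace an assessment that was not done. Severity is minor.

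**What to change.** Make three wording changes in Section 9.10:

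1. State that both CI-led and clinician-led decisions stop the study intervention only.
2. Limit the rule that no further data are contributed to participants who withdraw consent.
3. State that everyone else is offered the 12-week assessment and diary collection, and that any test judged unsafe may be left out.

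The clinician keeps full power to stop the exercise on clinical grounds, and the participant's right to withdraw is unchanged. The cost is the amendment itself and a little extra follow-up effort for anyone stopped.
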